Trigeminal nerve injuries can be caused by dental or oro-maxillofacial procedures and are increasingly common with growing demand for dental work. In a previous study among 8845 patients seen at the department of Oral & Maxillo-Facial Surgery of Leuven in 2013–2014, we identified 53 cases of iatrogenic nerve damage. (1) Patient ages ranged from 15–80 years (mean age, 42 years), and two-thirds were females. The average referral delay was 10 months, with a range of 1 day to 6.5 years. The most common damage site was the inferior alveolar nerve (IAN) (28 cases), followed by the lingual nerve (LN) (21 cases). Most nerve injuries were caused during third molar removal (24 cases), followed by implant placement (9 cases) and local anaesthesia injuries (9 cases). Endodontics-related injuries occurred in 3 cases. Pain symptoms were experienced by 54% of patients suffering IAN injury, compared to 10% of patients with LN injury. Persistent neurosensory disturbances (NSD) were identified in 60% of patients. While prevention remains the key issue, timely referral seems to be a critical factor. Moreover, research on burden of disease indicates a significant, and still underestimated, impact on QoL. (2-4)

Fundamental information on clinical presentation, symptoms, value of parameters measured during the clinical exam, investigations and use of medications or surgical repair have never been reported on a large number of patients. Most of the treatments are expert opinion based.

Currently, little or no research is published on Quality of Life (QoL), costs, productivity loss and medication use in patients with post-traumatic trigeminal neuropathy (PTN). We presume the impact of PTN on patients and society is underestimated and should be further studied and objectified.

2. Trial objectives and Design

2.1 Trial objectives

[figure not shown]
We aim to gain insights in the "burden of disease" of post-traumatic trigeminal neuropathy by performing a retrospective study analyzing patient records of all cases of post- traumatic, including iatrogenic, injury to branches of the trigeminal nerve seen at our department of Oral & Maxillofacial Surgery at UZ Leuven between January 2010 and October 2018 and possible subsequent post-traumatic neuropathy (PTN). The main endpoints are depicted underneath and focus on impact of the cause of injury, the injured branch of the nerve and the outcome (permanent versus temporary neurosensory disturbances) on healthcare costs, QoL, productivity loss and medication use.

To improve statistical power, the coded dataset from a retrospective study by prof. [name], co-investigator, will be provided to the principal investigator of the current study (dr. [name]) and merged with the dataset acquired in this study to further analyze presentation, symptoms, clinical exam, radiographic evaluation, treatments and outcome parameters. The dataset provided by prof. [name] was build by using the same inclusion

and exclusion criteria between January 2010 and October 2018. This should allow for a justified merging of both datasets. Statistical analysis will determine correlation of data.

Only looking at our own records of the department of Oral & Maxillofacial Surgery, UZ Leuven (thus not including the data from prof. [name]) we will evaluate healthcare costs, medication use and productivity loss in relation to the injury and Quality of Life (QoL) measured using the EQ5D survey. This survey has been used by several other authors investigating impact of orofacial pain and in studies evaluating burden of disease in relation to healthcare costs. (5-7) To achieve this goal, we will cooperate with the National Christian Sickness Fund (Christelijke Mutualiteiten, CM hereafter), see underneath for all details.

In summary:

2.2 Primary endpoints

- 1. What is the difference in total healthcare costs per patient and in total in patients with iatrogenic trigeminal nerve injury seen in our department according to cause of injury, injured nerve and outcome (temporary or permanent injury)?
 - A temporary injury will be defined as an injury that completely recovered with no more symptoms and clinical exam parameters within the normal limits during one of the consultations during the follow up period.
 - Permanent injury will be defined as an injury where no significant improvement in symptoms or clinical exam parameters was seen during one of the consultations during the follow up period.
- 2. What is the average productivity loss in days in patients with iatrogenic trigeminal nerve injury seen in our department according to cause of injury, injured nerve and outcome (temporary or permanent injury)?
- 3. Amount of medication use per medication class per patient in patients with iatrogenic trigeminal nerve injury seen in our department according to cause of injury, injured nerve and outcome (temporary or permanent injury)?

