2.3 Secondary endpoints

- 1. Are symptoms or clinical exam parameters (2 pointdiscrimination, directional sense, light touch, percentage of dermatome affected, pinprick threshold), MRCS classification and Sunderland classification predictive of a temporary or permanent injury? If so, which parameters can be withheld?
- 2. When an injury is present we will evaluate following parameters according to cause of injury, injured nerve branch and between temporary or permanent injury
 - Demographic data: age, gender
 - Symptoms, pain descriptors, interference with lifestyle
 - Clinical exam parameters (quantitative sensory testing)
 - Outcome & Follow-up: IHS criteria, surgical repair, use of medication
 - Social reimbursement rate and professional status
- 3. If data is present in the patient file regarding legal action taken by the patient against the caregiver who caused the injury this will be registered. We will evaluate how many patients undertook legal action and if they received compensation.
- 4. If sufficient follow up data is present, we will evaluate how long symptoms are present in case of a temporary injury and evaluate evolution of symptoms in relation to time.
- 5. Was imaging performed in light of the injury? If yes, what imaging modality was used (conebeam CT, CT, MRI, orthopantomogram) and did this influence treatment decisions?

- When looking at questionnaires applied in our department: are the results from the
 questionnaires comparable between the different causes of nerve injury, different affected
 branches? Are results comparable between patients suffering from a temporary or
 permanent injury? Following internationally validated questionnaires are part of routine
 examination of pain patients in our department and may be present in the patient KWS
 record:
 - McGill Pain Questionnaire
 - CPAQ-A
 - Brief Pain Inventory
 - EQ-5D
 - GAD-7
 - GCPS,
 - IES-DVL
 - OHIP-49
 - PainDetect
 - PHQ-9
 - PHQ-15
 - PSEQ
 - CPSI
 - IES
 - West Have-Yale Multidimensional Pain Questionnaire
 - Central sensitization inventory
- Is there a correlation between quality of life measured with EQ5D questionnaire and cause of injury, temporary versus permanent injuries, healthcare costs, productivity loss or medication use?

3. Selection and withdrawal of subjects

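### The section 2.2 definitions of temporary and permanent injury leave partial improvers without a class and ignore time since injury, although the analyses need a two-way split

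*Combined protocol and SAP*

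**What the plan says.** Section 2.2 (Primary endpoints) defines a temporary injury as "an injury that completely recovered with no more symptoms and clinical exam parameters within the normal limits during one of the consultations" and a permanent injury as "an injury where no significant improvement in symptoms or clinical exam parameters was seen during one of the consultations". Both definitions refer to the follow-up period, but its length is not stated anywhere.

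The label is then used as a two-level variable:

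- Section 2.1 gives as a main focus the impact of cause, nerve branch and "the outcome (permanent versus temporary neurosensory disturbances) on healthcare costs, QoL, productivity loss and medication use".
- Primary endpoints 1 to 3 (costs, productivity loss, medication use) are each broken down by cause, nerve and outcome.
- Secondary endpoint 1 in section 2.3 asks whether symptoms and examination findings are, along with the "MRCS classification and Sunderland classification predictive of a temporary or permanent injury". Other secondary items compare by outcome, including the question relating EQ-5D to "temporary versus permanent injuries, healthcare costs, productivity loss or medication use".
- Section 5 (Data Handling) models the label by logistic regression.

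The only condition on adequate follow-up is in secondary endpoint 4: "If sufficient follow up data is present, we will evaluate how long symptoms are present in case of a temporary injury". It has no figure and governs that endpoint alone.

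**The concern.** Complete recovery and no significant improvement are the two ends of a scale, and the text does not define the middle. Nor does it say what counts as significant, from what point improvement is judged, or whether failure in one domain is enough.

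Time is also missing. An unimproved patient seen briefly soon after injury can get the same label as one unrecovered after years. Patients are likely to enter at very different stages: in the department's earlier cohort, "The average referral delay was 10 months, with a range of 1 day to 6.5 years". That is time to referral, not follow-up length, but it shows how far the clocks can differ.

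At stake are the outcome comparisons in all three primary endpoints, the secondary comparisons by outcome, and the whole dependent variable of secondary endpoint 1. Without a written rule, whoever codes the records must decide where partial improvers and briefly followed patients go. That choice could differ between coders or between the two datasets, or be made after results are known.

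**Working it through.** **Inputs.** The two definitions (section 2.2); about 400 Leuven records (section 3); about 200 records for the sickness-fund analysis (section 7). The plan gives no figure for the share of partial improvers, so there is none to reproduce.

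**Step 1: enumerate the patterns.** Code each consultation N (no significant improvement), P (significant but incomplete) or R (complete recovery). Two consultations give 3 × 3 = 9 patterns.

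| Reading of the permanent definition | Temporary only | Permanent only | Both | Neither |
|---|---|---|---|---|
| Probable: improvement at no consultation | 5 (NR, RN, PR, RP, RR) | 1 (NN) | 0 | 3 (NP, PN, PP) |
| Literal: at least one consultation without improvement | 3 (PR, RP, RR) | 3 (NN, NP, PN) | 2 (NR, RN) | 1 (PP) |

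With three consultations (27 patterns) the probable reading gives 0 in both and 7 in neither; the literal reading gives 12 in both and 1 in neither.

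**Step 2: score symptoms and examination separately.** Each visit then has 3 × 3 = 9 states, so two visits give 81 patterns. Of these, 8 × 8 = 64 contain no complete recovery.

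| Reading | Meaning of 'or' | Both | Neither |
|---|---|---|---|
| Probable | failure in both domains | 0 | 64 − 1 = 63 |
| Probable | failure in either domain | 0 | 64 − 25 = 39 |
| Literal | failure in both domains | 2 | 7 × 7 = 49 |
| Literal | failure in either domain | 2 × 5 = 10 | 3 × 3 = 9 |

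If, on the probable reading, one and the same domain must fail at every visit, 64 − 17 = 47 patterns fall in neither. Partial improvement in both domains at both visits is unclassed in every case. A patient improved in one domain only is unclassed or permanent, depending on the meaning of 'or'. These are counts of possible patterns, not patient frequencies.

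**Step 3: scale, illustration only.** Let f be the share improving incompletely in both domains, assumed 10% to 30%. Unclassed on the probable reading = N × f.

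- Sickness-fund records: 200 × 0.10 = 20 to 200 × 0.30 = 60.
- Leuven records: 400 × 0.10 = 40 to 400 × 0.30 = 120.

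**Step 4: dependence on time, illustration only.** Assume that, among patients who eventually recover, time from injury to recovery is exponential with mean m of 6 to 12 months. The share already recovered at t months is 1 − exp(−t/m).

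- t = 3: 1 − exp(−3/12) = 0.22 to 1 − exp(−3/6) = 0.39.
- t = 24: 1 − exp(−24/12) = 0.86 to 1 − exp(−24/6) = 0.98.

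The same kind of patient would thus be seen recovered 22% to 39% of the time if last seen at 3 months, and 86% to 98% if last seen at 24 months.

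**Step 5: look for a repair elsewhere in the text.** The weight and offset in section 5 adjust for differing cost and productivity periods, not for the label. Multiple imputation there addresses missing values; a fully observed partial improver is undefined, not missing. The follow-up condition in secondary endpoint 4 does not reach the other endpoints.

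**The case against.** The strongest reply is that the authors plainly meant no improvement at any consultation, that the case report form (Addendum 1) may hold a coding rule, and that existing records can be recoded once the wording is clarified. Section 5 also urges caution over a single significant p-value.

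Part of this stands. On the probable reading there is no overlap. The form was not supplied, so a rule may exist, although section 2.2 does not point to it. Ease of recoding is a reason to settle the rule now. Caution over p-values does not define a class.

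Several stronger readings are tempting, and the documents do not support them:

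- *The classes overlap however they are read.* Overlap arises only on the literal reading.
- *Every partial improver is unclassed.* If failure in either domain is enough, a patient improved in only one domain can be permanent.
- *Single-visit patients cannot be classified.* The temporary definition needs no comparison visit. What is missing is the reference point for improvement in the permanent definition; improvement since injury might be documented by history.
- *Comparisons by cause and nerve are also compromised*, or, conversely, *are untouched*. Univariable comparisons do not use the label. Multivariable estimates may be affected if outcome is a covariate, and section 5 does not list covariates.
- *The earlier cohort gives the scale.* The background says "Persistent neurosensory disturbances (NSD) were identified in 60% of patients". It does not say that the rest recovered completely, or how many of the 60% had partly improved.

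**Conclusion.** The point holds as a defect in a stated rule, not merely as missing detail. The definitions are not exhaustive on either reading, and on the literal reading they are not exclusive either. Neither label uses time since injury or a minimum follow-up, so the label partly reflects when and how long a patient was observed.

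These conclusions rest on the text alone. The number of patients affected and the size and direction of any bias cannot be derived from the documents. The 20 to 60 of 200 records depends wholly on the assumed 10% to 30% and on the probable reading, and the recovery percentages depend on the assumed exponential times. The remaining uncertainty is whether the unseen case report form already contains a rule. The definition should be settled before records are coded.

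**What to change.** Replace the two definitions with one rule, applied once per patient to status at the last available consultation, in this order of precedence:

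1. Complete recovery.
2. Indeterminate: not recovered and last seen before a minimum time since injury, or improvement cannot be judged.
3. Partial improvement.
4. No significant improvement.

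The order makes the classes exclusive and exhaustive. Before coding, the investigators set:

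- the minimum time;
- the reference point for improvement, including documented improvement before referral;
- the meaning of 'significant';
- whether 'or' means either domain or both;
- whether partial improvement stands alone or is merged.

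If the case report form already holds such a rule, move it into the protocol.

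Apply the rule to the Leuven and King's College datasets where the data allow, and do not impute the label for known partial improvers. Report the outcome comparisons with partial improvement as a separate group. Repeat them with partial and indeterminate patients reassigned or excluded, as a sensitivity analysis; these reassignments do not bound a difference in costs. In the logistic model, use first-consultation predictors and adjust for time since injury and follow-up length. A time-to-recovery analysis with delayed entry at the first consultation is optional where visit dates exist; the documents do not confirm such dates for the King's College records.

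The cost is protocol wording and coding work on existing records. Some patients become indeterminate, and the binary comparison loses some precision.

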2.3 Secondary endpoints

- 1. Are symptoms or clinical exam parameters (2 pointdiscrimination, directional sense, light touch, percentage of dermatome affected, pinprick threshold), MRCS classification and Sunderland classification predictive of a temporary or permanent injury? If so, which parameters can be withheld?
- 2. When an injury is present we will evaluate following parameters according to cause of injury, injured nerve branch and between temporary or permanent injury
 - Demographic data: age, gender
 - Symptoms, pain descriptors, interference with lifestyle
 - Clinical exam parameters (quantitative sensory testing)
 - Outcome & Follow-up: IHS criteria, surgical repair, use of medication
 - Social reimbursement rate and professional status
- 3. If data is present in the patient file regarding legal action taken by the patient against the caregiver who caused the injury this will be registered. We will evaluate how many patients undertook legal action and if they received compensation.
- 4. If sufficient follow up data is present, we will evaluate how long symptoms are present in case of a temporary injury and evaluate evolution of symptoms in relation to time.
- 5. Was imaging performed in light of the injury? If yes, what imaging modality was used (conebeam CT, CT, MRI, orthopantomogram) and did this influence treatment decisions?

- When looking at questionnaires applied in our department: are the results from the
 questionnaires comparable between the different causes of nerve injury, different affected
 branches? Are results comparable between patients suffering from a temporary or
 permanent injury? Following internationally validated questionnaires are part of routine
 examination of pain patients in our department and may be present in the patient KWS
 record:
 - McGill Pain Questionnaire
 - CPAQ-A
 - Brief Pain Inventory
 - EQ-5D
 - GAD-7
 - GCPS,
 - IES-DVL
 - OHIP-49
 - PainDetect
 - PHQ-9
 - PHQ-15
 - PSEQ
 - CPSI
 - IES
 - West Have-Yale Multidimensional Pain Questionnaire
 - Central sensitization inventory
- Is there a correlation between quality of life measured with EQ5D questionnaire and cause of injury, temporary versus permanent injuries, healthcare costs, productivity loss or medication use?

3. Selection and withdrawal of subjects

Using underneath criteria patients will be included or excluded from this retrospective study. We estimate a sample size of 400 subjects within our department (UZ Leuven). Another 900 subjects are estimated to be included from the retrospective dataset provided by prof. [name] (King's College).

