3.2 Exclusion criteria

- Neuropathic pain in another region than the trigeminal nerve
- Neuropathic pain not caused by iatrogenic injury

4. Direct access to source data and documents

The selected CRF platform, CastorEDC (www.castoredc.com), permits trial-related monitoring, audit and EC review or regulatory inspection. Source data will be directly accessible to the rightful instance or person on request.

The trial will be conducted in compliance with the principles of the Declaration of Helsinki (current version), the principles of GCP and in accordance with all applicable regulatory requirements. This protocol and related documents will be submitted for review to the Ethics Committee.

The Investigator and the Participating Site shall treat all information and data relating to the Study disclosed to Participating Site and/or Investigator in this Study as confidential and shall not disclose such information to any third parties or use such information for any purpose other than the performance of the Study. All medical data, the data collected in the course of the study is treated with the utmost confidentiality. The medical secrecy, the international guidelines (ICH-GCP) and the Belgian legislation are complied with. The investigators undertake to respect the conditions in the European General Data Protection Regulation (2016/679 Europese Algemene Verordening Gegevensbescherming, AVG/GDPR) and the Belgian legislation on the protection of natural persons with regard to the processing of personal data.

5. Data Handling

Data will be analyzed by [name], statistician at Leuvens Biostatistiek en Statistische Bioinformatica Centrum. Following statistical methods will be applied.

Non-parametric analyses (Mann-Whitney U tests, Kruskal-Wallis tests, Spearman correlations, Fisher exact tests) will be used to compare in a univariable setting the primary and secondary endpoints between groups (e.g. type of nerve) and to evaluate relations between continuous and/or ordinal variables.

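### Symptoms, sensory tests and questionnaires are compared by cause and nerve with no assessment time set and no allowance for time since injury, so differences in stage can be mistaken for, or can hide, differences between causes or nerves

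*Combined protocol and SAP*

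**What the plan says.** Secondary endpoint 2 in section 2.3 reads: "When an injury is present we will evaluate following parameters according to cause of injury, injured nerve branch and between temporary or permanent injury". The parameters include symptoms, pain descriptors and quantitative sensory testing. A later item in 2.3 asks the same of a long list of questionnaires, EQ-5D among them, which are used because they "may be present in the patient KWS" record. Neither item says which consultation supplies the value or how long after injury it must fall.

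Section 5 (Data Handling) says that non-parametric tests "will be used to compare in a univariable setting the primary and secondary endpoints between groups (e.g. type of nerve"). Multivariable models are named there only for costs, productivity loss and the temporary/permanent classification. Differing periods are handled by a possible weight for costs and an offset for productivity loss. The only covariate named is centre, for the merged data.

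The background text before section 2 reports, for an earlier series at the same department: "The average referral delay was 10 months, with a range of 1 day to 6.5 years". It adds that "timely referral seems to be a critical factor". Item 4 of section 2.3 plans to study how symptoms evolve over time, if follow-up data suffice.

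**The concern.** Patients enter the study by being seen at the department. The criteria in sections 3.1 and 3.2 set no window of time since injury. The protocol itself expects the measured quantities to change: it defines temporary injuries as those that recover completely, and it plans to look at symptoms over time. A comparison of sensory tests or EQ-5D between causes may therefore set patients examined soon after injury against patients examined years later.

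If the mix of early and late assessments differs between the groups, the contrast contains stage as well as cause or nerve. It can then show a difference where there is none, or mask a real one. Adjusting for centre does not address a difference in delay between causes within a centre. Section 5 recognises the issue of unequal periods for costs and productivity loss, but offers nothing equivalent for symptoms, examination findings or questionnaires.

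**Working it through.** The plan contains no power calculation or effect size to reproduce; 400 (Leuven) and 900 (external) in section 3 are expected record counts. The check is a reading of how time is handled, plus two illustrations.

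**Inputs from the documents**
- Referral delay: mean 10 months, range 1 day to 6.5 years, in 53 cases from 2013–2014.
- Causes in that series: third molar removal 24, implant placement 9. Nerves: inferior alveolar 28, lingual 21.
- Significance level 0.05 (taken as two-sided).

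**Assumed inputs (not in the documents)**
- Illustration 1: the frequency of a specific sign early and late, and the share of each group examined early.
- Illustration 2: the correlation of the outcome with log time since injury (0.2 to 0.5), and the difference between nerves in mean log time (0, 0.25 or 0.5 SD).
- Both: the earlier series' mix applies to the new data.

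**Illustration 1: a specific sign, no true effect of cause**

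Expected proportion = (share early × frequency early) + (share late × frequency late).

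- Strong stage effect (80% early, 50% late). Cause A, 70% early: 0.7 × 0.80 + 0.3 × 0.50 = 0.71. Cause B, 30% early: 0.3 × 0.80 + 0.7 × 0.50 = 0.59. OR = (0.71/0.29)/(0.59/0.41) = 1.70; true OR 1.0.
- Weak stage effect (70% early, 60% late). A: 0.7 × 0.70 + 0.3 × 0.60 = 0.67. B: 0.3 × 0.70 + 0.7 × 0.60 = 0.63. OR = (0.67/0.33)/(0.63/0.37) = 1.19.

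Test: z = (pA − pB) / √[p̄(1 − p̄)(1/nA + 1/nB)], with p̄ the pooled proportion. For the expected mix, third molar v implant is 400 × 24/53 = 181 v 400 × 9/53 = 68 in Leuven, and 1300 × 24/53 = 589 v 1300 × 9/53 = 221 in the merged data.

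| Group sizes | Strong: z, p | Weak: z, p |
|---|---|---|
| 150 v 150 | 2.18, 0.03 | 0.73, 0.47 |
| 300 v 300 | 3.08, 0.002 | 1.03, 0.30 |
| 181 v 68 | 1.80, 0.07 | 0.59, 0.55 |
| 589 v 221 | 3.25, 0.001 | 1.07, 0.28 |

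**Illustration 2: a continuous outcome, no true effect of nerve**

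Mann-Whitney tests were simulated, 1000 runs per setting, with nerve groups of 400 × 28/53 = 211 v 400 × 21/53 = 158, and 1300 × 28/53 = 687 v 1300 × 21/53 = 515. The size of the bias is correlation × difference in log delay: 0.2 × 0.25 = 0.05 SD up to 0.5 × 0.5 = 0.25 SD.

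| Rate of p < 0.05 | N = 400 | N = 1300 |
|---|---|---|
| No difference in delay, unadjusted | 4.6–5.9% | 4.8–5.0% |
| Difference 0.25–0.5 SD, unadjusted | 8–63% | 13–99% |
| Log time in a linear model, all settings | 4.6–6.1% | 3.6–5.5% |

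The adjusted rows are a best case, because the model fitted is the one that generated the data. The N = 1300 results apply only to symptoms and examination findings; the questionnaires come from the department's own records.

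**The case against.** A reader might infer that stage differences will necessarily appear as effects of cause or nerve, or that referral delay is known to differ between causes. The documents support neither. They give no delay by cause or nerve, and illustration 2 shows no inflation when delay is equal. The 1 day to 6.5 years range describes 53 earlier cases; those years lie inside the study window, but the range only indicates the spread to expect.

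Other objections also stand in part:

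- Section 3.1 requires a diagnosed neurosensory deficit, so the presence of a deficit is largely fixed by selection. The bias concerns the severity of symptoms and signs or the frequency of a specific sign.
- Equal groups of 150 or 300 do not match the earlier mix of causes. At about 181 v 68 even the strong case gives p = 0.07, and the weak case is not significant at any size tried.
- Stratifying by time does not undo the selection of non-recovered patients among late referrals. If cause affects severity and severity affects referral, time since injury lies partly on the path from cause to outcome, and adjustment can add bias.
- Nothing says that the external dataset holds injury or examination dates.
- The case report form is a separate file (Addendum 1) and may record these dates. Their absence from 2.3 does not show that they are not collected.

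Two defences do not remove the point. Item 4 of section 2.3 brings in time, but as a separate, conditional question that adjusts no cause or nerve comparison. The caution that section 5 promises over isolated significant p-values deals with multiplicity, not bias. The endpoints affected are secondary and worded descriptively, which limits the harm.

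**Conclusion.** The point holds conditionally. As written, the plan fixes no assessment time for these secondary comparisons and tests them without regard to time since injury, although it expects symptoms to change. If time since injury differs by cause or nerve, the contrasts can be biased in either direction; if it does not, this source of bias is absent. The documents cannot settle which applies.

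Under the assumed inputs the spurious OR runs from 1.19 to 1.70, and whether it reaches p < 0.05 depends on group size. In illustration 2 the false-positive rate rises to between 8% and 63% at N = 400 when delay differs by 0.25 to 0.5 SD. These figures show what could happen; they do not estimate the bias in this study. The change is worth making because without time since injury a reader cannot tell stage from cause. The primary endpoints are not part of this point.

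**What to change.** In section 2.3:

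1. Define the index assessment as the first examination and the first questionnaire in the record.
2. Add time from injury to that assessment as a derived variable, and report it by cause, nerve and centre.
3. Describe EQ-5D by temporary or permanent outcome as quality of life at the index assessment by later outcome.

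In section 5, keep the univariable tests. Beside them, wherever dates exist, compare cause and nerve groups either stratified by time band (for example under 3, 3 to 12 and over 12 months) with a van Elteren or Cochran-Mantel-Haenszel test, or in a regression with log time since injury.

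State three limits: the adjustment does not remove selection of non-recovered late referrals; time since injury may lie partly on the path from cause to outcome; and, if the external dataset lacks dates, the adjusted analysis is confined to the Leuven records. Showing both results lets the reader see how much depends on the adjustment.

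The cost is some plan wording and one derived variable, which the department already obtained for its earlier series. Some injury dates will be missing, and intervals will be slightly wider. No further patients are needed.
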